#### **10.1.4 Data protection**

All personal data collected related to participants, Investigators, or any person involved in the study, which may be included in the Sponsor's databases, shall be treated in compliance with all applicable laws and regulations including the GDPR (General Data Protection Regulation). The study Sponsor is the Sanofi company responsible for ensuring compliance with this matter, when processing data from any individual who may be included in the Sanofi databases, including Investigators, nurses, experts, service providers, Ethics Committee members, etc.

When archiving or processing personal data pertaining to the Investigator and/or to the participants, the Sponsor takes all appropriate measures to safeguard and prevent access to this data by any unauthorized third party.

Data collected must be adequate, relevant and not excessive, in relation to the purposes for which they are collected. Each category of data must be properly justified and in line with the study objective.

Participant race and ethnicity will be collected in this study because these data are required by regulatory agencies (eg, on African American population for the FDA or on Japanese population for the Pharmaceuticals and Medical Devices Agency in Japan).

- Participants will be assigned a unique identifier by the Sponsor. Any participant records or datasets that are transferred to the Sponsor will contain the identifier only; participant names or any information which would make the participant identifiable will not be transferred to the Sponsor.
- The participant must be informed that his/her personal study-related data will be used by the Sponsor in accordance with local data protection law. The level of disclosure must also be explained to the participant as described in the informed consent.
- The participant must be informed that his/her medical records may be examined by Clinical Quality Assurance auditors or other authorized personnel appointed by the Sponsor, by appropriate IRB/IEC members, and by inspectors from regulatory authorities.

- The participant must be informed that his/her medical records may be examined by Clinical Quality Assurance auditors or other authorized personnel appointed by the Sponsor, by appropriate IRB/IEC members, and by inspectors from regulatory authorities.
- Participants must be informed that their study-related data will be used for the whole “drug development program”, ie, for this trial as well as for the following steps necessary for the development of the investigational product, including to support negotiations with payers and publication of results.

### **Protection of data related to professionals involved in the study**

- Personal data (eg, contact details, affiliation(s) details, job title and related professional information, role in the study, professional resume, training records) are necessary to allow Sanofi to manage involvement in the study and/or the related contractual or pre-contractual relationship. They may be communicated to any company of the Sanofi group (“Sanofi”) or to Sanofi service providers, where needed.
- Personal data can be processed for other studies and projects. At any time, objection to processing can be made by contacting the Sanofi Data Protection Officer (link available at [Sanofi.com](http://Sanofi.com)).
- In case of refusal to the processing of personal data by or on behalf of Sanofi, it will be impossible to involve the professionals in any Sanofi study. In case the professionals have already been involved in a Sanofi study, they will not be able to object to the processing of their personal data as long as they are required to be processed by applicable regulations. The same rule applies in case the professionals are listed on a regulatory agencies disqualification list.
- Personal data can be communicated to the following recipients:
  - Personnel within Sanofi or partners or service providers involved in the study
  - Judicial, administrative and regulatory authorities, in order to comply with legal or regulatory requirements and/or to respond to specific requests or orders in the framework of judicial or administrative procedures. Contact details and identity may also be published on public websites in the interest of scientific research transparency
- Personal data may be transferred towards entities located outside the Economic European Area, in countries where the legislation does not necessarily offer the same level of data protection or in countries not recognized by the European Commission as offering an adequate level of protection. Those transfers are safeguarded by Sanofi in accordance with the requirement of European law including, notably:
  - The standard contractual clauses of the European Commission for transfers towards our partners and service providers,
  - Sanofi’s Binding Corporate Rules for intra-group transfers.
- Professionals have the possibility to lodge a complaint with Sanofi leading Supervisory Authority, the “Commission Nationale de l’Informatique et des Libertés” (CNIL) or with any competent local regulatory authority.

- Personal data of professionals will be retained by Sanofi for up to thirty (30) years, unless further retention is required by applicable regulations.
- In order to facilitate the maintenance of Investigators personal data, especially if they contribute to studies sponsored by several pharmaceuticals companies, Sanofi participates in the Shared Investigator Platform (SIP) and in the TransCelerate Investigator Registry (IR) project (<https://transceleratebiopharmainc.com/initiatives/investigator-registry/>). Therefore, personal data will be securely shared by Sanofi with other pharmaceutical company members of the TransCelerate project. This sharing allows Investigators to keep their data up-to-date once for all across pharmaceutical companies participating in the project, with the right to object to the transfer of the data to the TransCelerate project.
- Professionals have the right to request the access to and the rectification of their personal data, as well as their erasure (where applicable) by contacting the Sanofi Data Protection Officer: Sanofi DPO - [name] (to contact Sanofi by email, visit <https://www.sanofi.com/en/our-responsibility/sanofi-global-privacy-policy/contact>).

#### **10.1.5 Committee structure**

##### **Dose Selection Committee**

The dose selection committee will determine the dose for Part A, Cohorts 2 and 3, and Part B. The committee will also determine whether to open Cohort 3. The committee will be comprised of (at a minimum) the Study Medical Manager, Clinical Research Director, Pharmacokineticist, Statistician, Global Safety Officer, and overall study Principal Investigator.

#### **10.1.6 Dissemination of clinical study data**

Sanofi shares information about clinical trials and results on publically accessible websites, based on company commitments, international and local legal and regulatory requirements, and other clinical trial disclosure commitments established by pharmaceutical industry associations. These websites include clinicaltrials.gov, EU clinicaltrialregister (eu.ctr), and sanofi.com, as well as some national registries.

In addition, results from clinical trials in patients are required to be submitted to peer-reviewed journals following internal company review for accuracy, fair balance and intellectual property. For those journals that request sharing of the analyzable data sets that are reported in the publication, interested researchers are directed to submit their request to [clinicalstudydatarequest.com](http://clinicalstudydatarequest.com).

Individual participant data and supporting clinical documents are available for request at [clinicalstudydatarequest.com](http://clinicalstudydatarequest.com). While making information available we continue to protect the privacy of participants in our clinical trials. Details on data sharing criteria and process for requesting access can be found at this web address: [clinicalstudydatarequest.com](http://clinicalstudydatarequest.com).

## **Professionals involved in the study or in the drug development program**

Sanofi may publicly disclose, and communicate to relevant authorities/institutions, the funding, including payments and transfers of value, direct or indirect, made to healthcare organizations and professionals and/or any direct or indirect advantages and/or any related information or document if required by applicable law, by regulation or by a code of conduct such as the “EFPIA Code on Disclosure of Transfers of Value from Pharmaceutical Companies to Healthcare Professionals and Healthcare Organisations”.

### **10.1.7 Data quality assurance**

- All participant data relating to the study will be recorded on printed or electronic CRF unless transmitted to the Sponsor or designee electronically (eg, laboratory data). The Investigator is responsible for verifying that data entries are accurate and correct by physically or electronically signing the CRF.
- The Investigator must maintain accurate documentation (source data) that supports the information entered in the CRF.
- The Investigator must permit study-related monitoring, audits, IRB/IEC review, and regulatory agency inspections and provide direct access to source data documents.
- Monitoring details describing strategy (eg, risk-based initiatives in operations and quality such as Risk Management and Mitigation Strategies and Analytical Risk-Based Monitoring), methods, responsibilities and requirements, including handling of noncompliance issues and monitoring techniques (central, remote, or on-site monitoring) are provided in separate study documents.
- The Sponsor or designee is responsible for the data management of this study including quality checking of the data.
- The Sponsor assumes accountability for actions delegated to other individuals (eg, Contract Research Organizations).
- Study monitors will perform ongoing source data verification to confirm that data entered into the CRF by authorized site personnel are accurate, complete, and verifiable from source documents; that the safety and rights of participants are being protected; and that the study is being conducted in accordance with the currently approved protocol and any other study agreements, ICH GCP, and all applicable regulatory requirements.
- Records and documents, including signed ICFs, pertaining to the conduct of this study must be retained by the Investigator for 25 years after the signature of the final study report unless local regulations or institutional policies require a longer retention period. No records may be destroyed during the retention period without the written approval of the Sponsor. No records may be transferred to another location or party without written notification to the Sponsor.

#### **10.1.8 Source documents**

- Source documents provide evidence for the existence of the participant and substantiate the integrity of the data collected. Source documents are filed at the Investigator's site.
- Data reported on the CRF or entered in the eCRF that are transcribed from source documents must be consistent with the source documents or the discrepancies must be explained. The Investigator may need to request previous medical records or transfer records, depending on the study. Also, current medical records must be available.

#### **10.1.9 Study and site start and closure**

The study start date is the date on which the clinical study will be open for recruitment of participants.

The Sponsor or designee reserves the right to close a study site or terminate the study at any time for any reason at the sole discretion of the Sponsor. Study sites will be closed upon study completion. A study site is considered closed when all required documents and study supplies have been collected and a study-site closure visit has been performed.

The Investigator may initiate study-site closure at any time, provided there is reasonable cause and sufficient notice is given in advance of the intended termination.

Reasons for study termination by the Sponsor, as well as reasons for the early closure of a study site by the Sponsor or Investigator may include but are not limited to:

- For study termination:
  - Information on the product leads to doubt as to the benefit/risk ratio
  - Discontinuation of further study intervention development
- For site termination:
  - Failure of the Investigator to comply with the protocol, the requirements of the IRB/IEC or local health authorities, the Sponsor's procedures, or GCP guidelines
  - Inadequate or no recruitment (evaluated after a reasonable amount of time) of participants by the Investigator
  - Total number of participants included earlier than expected

If the study is prematurely terminated or suspended, the Sponsor shall promptly inform the Investigators, the IECs/IRBs, the regulatory authorities, and any contract research organization(s) used in the study of the reason for termination or suspension, as specified by the applicable regulatory requirements. The Investigator shall promptly inform the subject and should assure appropriate subject therapy and/or follow-up.

## **Dose limiting toxicity (DLT) and study stopping rules**

### DLT rules for Part A

- A DLT in Part A is defined as a Grade 3 or higher AE, unless clearly attributable to wAIHA or clearly unrelated to the study drug
- If 1 DLT occurs in any cohort, the dose for the next cohort cannot be increased
- If >1 DLT occurs in any cohort, the dose for the next cohort must be reduced

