## 4 STUDY DESIGN

### 4.1 OVERALL DESIGN

This is a Phase 1b/2 open-label, non-randomized, multicenter study to evaluate the safety, pharmacokinetics, and efficacy of subcutaneous isatuximab in adults with wAIHA. The study will be conducted in 2 parts: Part A for safety and dose-finding, and Part B for assessment of the efficacy of the selected dose regimen. Approximately 17 to 23 participants are expected to be enrolled, depending on the number of participants in Part A who receive the regimen chosen for Part B.

Part A will have 2 to 3 cohorts. Cohort 1 consists of 3 participants who will receive 2 doses of isatuximab 140 mg (1 mL) SC administered 2 weeks apart. Cohort 2 can open following a review of available safety, pharmacokinetic (PK), and pharmacodynamic (PD) data after the 3 participants in Cohort 1 complete the Day 43 visit. Cohort 2 will consist of 3 participants who will receive isatuximab SC given every 2 weeks through Day 71 (total of 6 doses). The dose for Cohort 2 may be 70 mg (0.5 mL), 140 mg (1 mL), or 280 mg (2 mL), determined based on the safety profile, PK, and PD observed in Cohort 1.

Once the 3 participants in Cohort 2 have completed the Day 85 visit, an analysis of the available safety, PK, and PD data will be performed, and a decision will be made to either enroll 3 participants as an additional optional dose-finding cohort (Cohort 3) in which a dose up to 560 mg (4 mL) can be investigated, or to open Part B. If Cohort 3 is enrolled, Part B will open once available safety, PK, and PD data through the Day 85 visit from those participants have been reviewed.

Participants in Cohort 1 who experience no response by the end of the treatment period, or a response that subsequently wanes while still in follow up, can be retreated, after completing the Day 43 visit, with 6 administrations of the dose selected for the Cohort 2, Cohort 3, or Part B. Such participants will continue to be followed for at least 24 weeks from the first retreatment dose, but their response to the additional doses will not be included for efficacy analyses.

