For the review of data between each cohort, the safety data will consist of clinical and laboratory parameters and adverse events. Unacceptable toxicity is defined as any verified Grade 4 AE or laboratory abnormality (except infusion reactions [IRs]) occurring during the treatment period, unless due to the underlying disease or due to a cause unrelated to the IMP, if confirmed by the Sponsor and Investigators. PK data will include standard PK parameters, with a focus on isatuximab exposure ( $C_{max}$  and  $AUC_{0-2\text{ week}}$ ). PD data will include hemoglobin levels, markers of hemolysis, and immune cell profiling.

A decision to de-escalate the dose between cohorts will primarily be based on safety signals, while a decision to dose escalate will primarily be based on an insufficient hemoglobin response. Additional PD and PK data will be used to help guide these decisions. While it is anticipated that dose selection for each cohort will occur after all participants in the previous cohort have completed the Day 43 (Part A, Cohort 1) or Day 85 (Part A, Cohorts 2 and 3) visits, in certain circumstances such decisions may be made earlier if clear safety or efficacy signals emerge. All

decisions regarding dose levels and the opening of new cohorts will be made by Sponsor representatives and the Principal Investigator at dose selection meetings. See [Section 10.1.5](#) for the composition of the dose selection committee.

Part B will consist of 8 to 14 participants who will receive isatuximab SC every 2 weeks for a total of 6 doses, at a dose to be determined by the totality of safety, PK, and PD data available from all participants in Part A. The maximum allowable dose in Part B is 560 mg. Approximately 14 participants in the study will receive the isatuximab regimen selected for Part B. Thus, the number of participants in Part B may range from 8 to 14, depending on the number of participants in Part A who received that same regimen in the second or third cohort.

All participants will receive isatuximab subcutaneously. The screening period is 28 days, followed by a treatment period of 42 days (6 weeks) for Cohort 1 or 84 days (12 weeks) for the other participants in the trial. All participants will be followed for at least 24 weeks from the first isatuximab dose. The total length of the study, including screening, is 28 weeks.

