### **6.6.1 Retreatment criteria**

Participants in Cohort 1 may receive additional study interventions if they meet retreatment criteria and agree to be retreated. The retreatment criteria are as follows:

- No response in hemoglobin (R) by end of the treatment period (Day 43).
- A hemoglobin response (R) that subsequently wanes prior to the end of study, with hemoglobin falling below 10 g/dL on 2 occasions at least 7 days apart

These participants will be followed for a total of 24 weeks from the first retreatment dose, but the retreatment period will not be included in PK, PD, or efficacy analyses.

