## 7 DISCONTINUATION OF STUDY INTERVENTION AND PARTICIPANT DISCONTINUATION/WITHDRAWAL

### 7.1 DISCONTINUATION OF STUDY INTERVENTION

#### 7.1.1 Definitive discontinuation

In rare instances, it may be necessary for a participant to permanently discontinue study intervention (definitive discontinuation). If study intervention is definitively discontinued, the participant will remain in the study to be evaluated for safety.

Pregnancy will lead to definitive treatment discontinuation in all cases.

Discontinuation of study intervention for abnormal liver function should be considered by the Investigator when a participant meets one of the conditions outlined in [Section 10.6](#) or if the Investigator believes that it is in best interest of the participant.

Treatment with the IMP should be discontinued in any of the following cases:

- At the participant's request, at any time and irrespective of the reason (participant's decision), or at the request of their legally authorized representative without any effect on their care. "Legally authorized representative" is considered to be an individual or judicial or other body authorized under applicable law to consent on behalf of a prospective patient to the patient's participation in the procedure(s) involved in the research.
- If, in the Investigator's opinion, continuation of the IMP would be detrimental to the participant's well-being, such as:
  - unacceptable AE,
  - poor compliance to the study protocol,
  - any other reason such as intercurrent illness that prevents further administration of IMP (will be specified).
- Participant is lost to follow-up.

See the SoA for data to be collected at the time of intervention discontinuation and follow-up and for any further evaluations that need to be completed.

Any abnormal laboratory value that could result in treatment discontinuation will be immediately rechecked for confirmation (within 24 hours) before making a decision regarding definitive discontinuation of the IMP for the concerned participant.

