### DLT rules for Part B

- A DLT in Part B is defined as a Grade 4 or higher AE, unless clearly attributable to wAIHA or clearly unrelated to the study drug
- If >1 DLT occurs in Part B, a dosing and enrollment hold will occur. The hold may be lifted if the benefit/risk ration of the study is still deemed to be favorable by applicable competent authorities

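### More than one DLT in a Part A cohort only lowers the next cohort's dose: Cohort 1 retreatment at the affected dose stays open, and Part B's hold at more than one Grade 4+ DLT has no Part A counterpart

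*Protocol*

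**What the plan says.** **Part A.** Protocol 10.1.9 (DLT rules for Part A) counts Grade 3 or higher adverse events, unless clearly due to wAIHA or clearly unrelated to the drug. One DLT bars a dose increase for the following cohort. Beyond that: "If >1 DLT occurs in any cohort, the dose for the next cohort must be reduced". Nothing is said about participants still being dosed at the affected dose.

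**Part B.** The threshold grade is higher: "A DLT in Part B is defined as a Grade 4 or higher AE", with the same attribution exceptions. The consequence is immediate: "If >1 DLT occurs in Part B, a dosing and enrollment hold will occur".

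**Retreatment.** Protocol 6.6.1 states: "Participants in Cohort 1 may receive additional study interventions if they meet retreatment criteria and agree to be retreated". The criteria are no hemoglobin response by Day 43, or a response that later wanes. Section 4.1 says that such participants "can be retreated, after completing the Day 43 visit, with 6 administrations of the dose selected for the Cohort 2", and goes on to allow the Cohort 3 or Part B dose as well. Section 6.6 names the same three doses. None of these sections mentions DLTs, either at the retreatment dose or in the participant concerned.

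**Other safeguards.** Section 4.1 defines unacceptable toxicity for the between-cohort review as a verified Grade 4 event or laboratory abnormality (infusion reactions and unrelated causes excepted), but attaches no action to it. It also allows dose decisions ahead of schedule: "in certain circumstances such decisions may be made earlier if clear safety or efficacy signals emerge". Section 7.1.1 says that IMP should stop if, in the investigator's opinion, "continuation of the IMP would be detrimental" to the participant. SAEs reach the sponsor within 24 hours (8.3.1), and life-threatening or fatal SUSARs reach authorities within 7 days (8.3.4). The sponsor may end the study at any time (10.1.9).

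**The concern.** Safety is the primary objective of Part A, and Protocol 2.3 states that there are no safety data outside oncology. A rule that closes a dose to the next cohort expresses a judgement that the dose was not well enough tolerated. As written, that judgement does not reach two groups already in the study: Cohort 1 participants about to begin, or part-way through, six retreatment doses at that level, and the remaining members of the affected cohort when the events were Grade 4 or worse. For that second situation the protocol does mandate a hold, but only in Part B.

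At stake is avoidable exposure to a dose that the protocol's own rule has ruled out for newcomers.

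**Working it through.** The plan states no figure on this point, so there is none to reproduce. The check is a comparison of rules, then arithmetic on exposure, timing and the cost of a pause.

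**1. The rules side by side**

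| Event | Part A | Part B |
|---|---|---|
| More than one DLT, all Grade 3 | Next cohort's dose lowered | Not counted as DLTs |
| More than one DLT, Grade 4 or higher | Next cohort's dose lowered; no hold | Dosing and enrollment hold |

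Only the second row compares like with like.

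**2. Where the retreatment gap arises.** More than one DLT in Cohort 1 does not create it, because the Cohort 2 dose must then be lower. More than one DLT in Cohort 2 or 3 does: the next dose must fall, but retreatment at the affected dose remains allowed. A lower dose may also be available for retreatment; nothing requires its use.

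**3. Exposure left open**
- Retreatment: 6 administrations per participant. With 3 participants in Cohort 1, the ceiling is 3 × 6 = 18. SAP 1.3 records one retreated participant (280 mg, six doses), which is 6.
- Within a six-dose cohort, after dose *k*, assuming parallel dosing and that those with a DLT stop: 6 − *k* = 5 to 1 administrations for *k* = 1 to 5 if the DLTs are in two participants; 2(6 − *k*) = 10 to 2 if both are in one. The rule counts DLTs, not participants.

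**4. Timing, from the visit schedule in 1.3 and the planned reviews in 4.1**
- Cohort 2 can open once Cohort 1 has completed Day 43. Follow-up remaining to Day 169: 169 − 43 = 126 days.
- Cohort 3 can open after Cohort 2's Day 85, which is 84 days after its first dose: 43 + 84 = Cohort 1 Day 127. Remaining: 169 − 127 = 42 days.
- Both are best cases. They apply to the last Cohort 1 enrollee, with no time for data review or recruitment. Earlier enrollees have less, and the DLTs must also have time to occur.
- The waning criterion must be met before the end of study, so these windows limit it. The Day 43 non-response criterion has no stated deadline.
- An early dose decision under 4.1 could bring either opening forward.

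**5. How often a Grade 4+ pause would occur.** The documents give no DLT rate, so *p*, the chance that a participant has a Grade 4+ DLT, is assumed. Participants are taken as independent, with at most one DLT each and the same *p* in three cohorts of three.

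Per cohort: P = 3*p*²(1 − *p*) + *p*³. Over three cohorts: 1 − (1 − P)³.

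| *p* | P per cohort | At least one pause in three |
|---|---|---|
| 0.02 | 0.0012 | 0.0035 |
| 0.05 | 0.0072 | 0.0216 |
| 0.10 | 0.0280 | 0.0817 |

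If several DLTs in one participant count (Poisson, mean −ln(1 − *p*) each), the three-cohort figures are 0.0053, 0.0317 and 0.1169.

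**The case against.** **A three-person cohort needs no hold.** With DLTs in two participants, one unaffected person remains, and 7.1.1 already lets the investigator stop that person's treatment. New cohorts open only after data review. This has force against a broad pause and shows that the second gap is small in numbers. It does not answer the retreatment gap, which brings in people from outside the affected cohort.

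**Safeguards exist, and retreatment is permissive.** Investigators, the sponsor and the early-decision clause could each stop dosing, and nobody has to be retreated at the affected dose. A reader might infer that Part A has no protection against continued dosing; that is not so. What stands is that these measures are discretionary, individual-level or reporting-only, whereas Part B has a mandatory hold.

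**Part B is not simply stricter.** A reader might infer from the hold that Part A is the laxer part throughout. The documents do not support that: Part A counts Grade 3 events, which Part B ignores. Nor do they show that Part A needs a pause at more than one Grade 3+ DLT. With three people on a six-dose regimen, two Grade 3 events in one participant could interrupt treatment of refractory disease in the other two. That pause is optional and is not part of this point.

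**Prior experience is substantial.** Section 2.3 cites about 1652 people treated intravenously, 2.3.1 cites subcutaneous use at 1000 mg, and 4.2 caps the dose at about half of that used in myeloma. This makes the trigger less likely, but does not say what should follow if it is met.

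**Conclusion.** The point holds as a gap in the rules as written, and is a cheap improvement. After more than one DLT at a Cohort 2 or 3 dose, no rule bars six-dose retreatment of Cohort 1 participants at that dose; and more than one Grade 4+ DLT mandates a hold in Part B but not in Part A.

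The retreatment gap matters mainly for the Cohort 2 dose. The Cohort 3 route is narrow for waning responders, though the open-ended Day 43 criterion keeps it from closing completely. These conclusions rest on the planned timing; the pause frequencies rest on assumed DLT rates and are not evidence of harm.

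A reader might infer that the participant retreated at 280 mg was dosed after DLTs at that level, or that the early stop reflected toxicity. The SAP supports neither. It gives no DLT counts and no reason for stopping. If the 140, 280 and 560 mg labels follow cohort order, they suggest that no reduction was triggered after either of the first two cohorts; they cannot speak to the last. No harm is shown in this trial.

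**What to change.** Add to Protocol 6.6.1:

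> *Cohort 1 retreatment may not start or continue at a dose, or higher, at which >1 DLT has occurred, unless the dose selection committee has reviewed the data and documented its agreement. The same agreement is needed to retreat a participant who had a DLT.*

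Add to Protocol 10.1.9, DLT rules for Part A:

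> *If >1 Grade 4 or higher DLT occurs at a dose, dosing and enrollment at that dose or higher are paused until the dose selection committee has documented its decision.*

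The committee already exists (10.1.5), and both additions leave it the final decision, so they do not conflict. The DLT definitions and cohort sizes stay as they are.

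**Cost.** A protocol amendment; the amendment history shows that these rules were last updated at a regulator's request. No extra participants or visits are needed. Limiting retreatment costs no planned efficacy estimate, because retreatment data are kept out of the analyses other than listings (Protocol 9.4.1, SAP 1.3). The real downside is a rare pause that could delay or cost doses for remaining participants. Section 9.2.2 pools Part A participants by dose and number of administrations received, so a lost dose could also affect pooling with Part B. The SAP records that the study stopped early without Part B, so the practical use of the wording is in any protocol that carries these rules forward.
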